## 2 Abbreviations and Definitions

AE	Adverse Event
CRF	Case Report Form
CSF	Cerebrospinal fluid
GAS	Group A streptococcus
GBS	Group B streptococcus
IMP	Investigational Medical Product
HPS	Hypertrophic pyloric stenosis
HAZ	Height-for-age z-score
LBW	Low birth weight (<2.5kg)
MUAC	Mid upper arm circumference
RR	Risk ratio
SAP	Statistical Analysis Plan
SD	Standard deviation
VLBW	Very low birth weight (<1.5kg)
WAZ	Weight-for-age z-score
WHZ	Weight-for-height z-score

## 3 Introduction

### 3.1 Preface

The study aims to assess the impact of azithromycin treatment during labour on neonatal mortality as well as maternal and neonatal sepsis and infant growth. If successful, this simple intervention could be implemented through the health system at the most peripheral level of care. It has the potential to achieve wide coverage in sub-Saharan Africa where low-cost interventions to reduce neonatal mortality are urgently needed.

### 3.2 Purpose of the analyses

These analyses will assess the efficacy and safety of the intervention and will be included in peer-reviewed publications of the trial results.

### 3.3 Study Objectives

(ICH E3; 8)

#### Primary objective

To assess the effect of giving one oral dose of AZI (2g) during labour on the combined endpoint of neonatal sepsis and mortality. Deaths due to severe birth asphyxia, very low birth weight (VLBW) and major congenital malformations will be excluded from the composite endpoint.

#### Secondary objectives

To examine the effect of the intervention on other clinical endpoints and microbiological endpoints in the neonate and mother.

#### Safety objectives

To evaluate the safety of the intervention through active and passive surveillance for adverse events (AE) in mothers and newborns during the 28-day follow-up period. All newborns with history of projectile vomiting will be thoroughly assessed for hypertrophic pyloric stenosis (HPS).

### 3.4 Endpoints

(ICH E9; 2.2.2)

#### **Primary endpoint:**

Neonatal sepsis or death within 28 days of birth, with the latter excluding deaths due to severe birth asphyxia, very low birth weight (VLBW) or a major congenital malformation.

#### **Secondary endpoints:**

##### Neonates (first 28 days of life)

1. Sepsis alone
2. Neonatal deaths, excluding those due to severe birth asphyxia, VLBW and major congenital malformations
3. Culture-confirmed sepsis
4. All-cause hospitalisation
5. All-cause mortality among VLBW

6. Skin infections
7. Bacterial conjunctivitis
8. Umbilical cord infections
9. Clinical malaria
10. Use of antibiotics during the neonatal period

#### Anthropometric cohort (1,000 infants) – follow-up for 12 months

1. All-cause mortality
2. Malnutrition (day 28, 6 and 12 months) – Height-for-age z-score (HAZ), weight-for-age z-score (WAZ), weight-for-height z-score (WHZ), body mass index-for-age, head circumference-for-age, and mid-upper arm circumference for age (MUAC)

#### Mothers (during the 28 days follow-up)

1. Post-partum sepsis
2. Post-partum mastitis
3. Post-partum malaria
4. Post-partum fever
5. Post-partum antibiotic use
6. Post-partum hospitalisation
7. Post-partum mortality

#### Hospitalised neonates

1. *Streptococcus pneumoniae* in nasopharyngeal swabs
2. *Klebsiella* species in nasopharyngeal swabs
3. *Escherichia coli* in rectal swabs
4. *Pseudomonas* species in rectal swabs
5. *Staphylococcus aureus* in oropharyngeal swabs
6. Group B Streptococcus in oropharyngeal swabs
7. Group A Streptococcus in oropharyngeal swabs

#### Carriage cohort (500 mothers and their children –250 pairs per country)

1. *S. pneumoniae* in infant nasopharyngeal swabs
2. *Klebsiella* in infant nasopharyngeal swabs
3. *E. coli* in infant rectal swabs
4. *Klebsiella* in infant rectal swabs
5. *Pseudomonas* in infant rectal swabs
6. *S. aureus* in infant oropharyngeal swabs

7. GBS in infant oropharyngeal swabs
8. GAS in infant oropharyngeal swabs
9. *S. aureus* in breast milk samples
10. GBS in breast milk samples
11. GAS in breast milk samples
12. *E. coli* in breast milk samples
13. *Pseudomonas* in breast milk samples
14. *Klebsiella* in breast milk samples
15. *E. coli* in NPS collected from women
16. *S. pneumoniae* in NPS collected from women
17. *Klebsiella* in NPS collected from women
18. *S. aureus* in OPS collected from women
19. GBS in OPS collected from women
20. GAS in OPS collected from women
21. Resistance to AZI, oxacillin and amoxicillin among isolates of *S. aureus*
22. Resistance to AZI, oxacillin and amoxicillin among isolates of GBS
23. Resistance to AZI, oxacillin and amoxicillin among isolates of GAS
24. Resistance to AZI, oxacillin and amoxicillin among isolates of *S. pneumoniae*
25. Resistance to AZI, oxacillin and amoxicillin among isolates of *Klebsiella*

### Safety endpoints

1. Solicited and unsolicited AEs observed or reported in mothers in the 28 days after treatment.
2. Solicited and unsolicited AEs in newborns observed or reported in the first 28 days after birth.
3. AEs reported among infants followed up to 1 year.

## 4 Study Methods

### 4.1 General Study Design and Plan

(ICH E3; 9)

PregnAnZI-2 was a phase III, double-blinded, placebo-controlled randomized clinical trial in which women in labour were randomized to either a single 2g dose of oral AZI or placebo. The study recruited 12,000 women (6750 in The Gambia and 5250 in Burkina Faso).

In The Gambia, women were recruited in two health facilities—Bundung Maternal and Child Health Hospital and Serrekunda Health Centre. In Burkina Faso, recruitment took place in a number of health facilities in Nanoro and Yako health districts.

Women were consented during the antenatal care visits but the study number (randomisation number) was only assigned after screening during labour, provided the woman met the necessary inclusion and exclusion criteria for participation.

Before March 23rd 2020, women and their newborns were visited at 28 day (either at home or at the health facility). After March 23rd 2020, women were not visited at home because of the risk of SARS-CoV-2 transmission, instead the day 28 interview was conducted by telephone. Cases of maternal and neonatal sepsis were identified through passive case detection at the study health facilities during the 28-day follow up period.

Additional scheduled visits at 6 and 12 months were performed for the first 2,000 women recruited (half in The Gambia and half in Burkina Faso) to assess infant anthropometrical measurements, hospitalization and all-cause mortality.

Carriage samples (recto-vaginal swabs, NPS, OPS, rectal swabs and breast milk samples) were collected from 500 randomly selected mother-newborn dyads (or triads in the case of twins). The samples were collected at day 0, day 6, day 28 and at 4 months.

## 4.2 Inclusion-Exclusion Criteria

(ICH E3; 9.3. ICH E9; 2.2.1)

### Inclusion criteria

- Pregnant women in labour
- Attending the study health facilities for delivery
- Aged  $\geq 16$  years
- Previously given consent and willing to continue participation

### Exclusion criteria

- Known HIV infection
- Any chronic or acute conditions that might interfere with the study as judged by the research clinician

- Planned travel out of the catchment area during the following 28 days
- Planned caesarean section or known referral
- Known severe congenital malformation
- Intrauterine death confirmed before randomisation
- Known allergy to macrolides
- Known to have taken drugs that prolong QT interval—such as chloroquine, quinine, piperazine, erythromycin—during the last 2 weeks
- Already participating in another trial

### 4.3 Blinding and randomisation

(ICH E3; 9.4.3, 9.4.6. ICH E9; 2.3.1, 2.3.2)

A list of randomization numbers was prepared by an independent statistician at the IDIFARMA contract development and manufacturing company using block randomisation. A five-digit number + control number was used, with the first digit denoting country (The Gambia = 1 and Burkina Faso =2). For example, in The Gambia a randomisation number is of the form |1||X||X||X||X||X|.

The randomisation list was used to number blister packs of 4 blisters of AZI or placebo (the dose of AZI or placebo was administered as 4 x 0.5g tablets) which were stored in boxes of 25–50 blister packs. Within each box, the blister packs were ordered sequentially.

Boxes were allocated to health facilities; therefore, the randomisation is stratified by health facility.

Note that the randomization numbers are not ordered by recruitment date because each box was assigned to a specific health facility, and women were recruited in several health facilities simultaneously.

Sealed envelopes containing the treatment allocation are kept at the study sites for emergency cases. In addition, a copy of the randomisation is being held by the DSMC.

### 4.4 Study Variables

(ICH E3; 9.5.1. ICH E9; 2.2.2)

The study activities for all mother–newborn dyads/triads enrolled in the study are summarised in the table below (Table 1). In the subset enrolled in the carriage sub–study (n=250 per country), additional home visits were conducted at day 6 and 4 months, and in the subset enrolled in the anthropometrical sub–study (n=1,000 per country) additional home visits were conducted at 6 and 12 months. Surveillance for deaths, sepsis and adverse events was up to day 28 for all participants. In addition, for participants in the carriage sub–study, surveillance for deaths and serious adverse events extended to 4 months, and for participants in the anthropometric sub–study surveillance extended to 12 months.

Note that day 0 is the date of birth rather than date of randomisation as in the study protocol. We have chosen to re–define follow up time as time from birth rather than time from randomisation to ensure that the definition of neonatal sepsis—one of the components of the primary outcome—is consistent with the standard definition.

**Table 1** Summary of study activities

	Pregnancy	Day 0  or Day -1 or Day 1	Day 28 (±4days)
Sensitisation & consent	X		
Health facility visit for delivery		X	
Review of inclusion & exclusion criteria		X	
Randomisation & treatment		X	
Discharge review		X	
Active follow–up (home visit)			X
Passive surveillance 		—————→	

Day 0 is defined to be the day of birth. Note that randomisation and discharge might not occur on the same day as the delivery.

Passive surveillance for adverse events, mortality and sepsis. The surveillance period extends to 4 months for mothers and children participating in the carriage sub–study and to 12 months for children participating in the anthropometrical sub–study.

**Table 2** Carriage samples collected from mother–newborn pairs (n=500; 250/country) enrolled in the carriage sub–study

	Day 0  (or Day –1)	Day 6 (±2 days)	Day 28 (±4 days)	4 Months (±2 weeks)
Mother				
Recto–Vaginal	X 			
Nasopharyngeal	X 	X		
Oropharyngeal	X 	X		
Breast milk		X	X	X
Newborn				
Nasopharyngeal	X 	X	X	X
Oropharyngeal	X 	X	X	X
Rectal	X 	X	X	X

Samples collected on the day of birth (baby) or randomisation (mother) were collected at the health facility. Note that randomisation often occurred the day before delivery.  
Samples collected before treatment  
Samples collected within 4 hours of delivery/birth

### Baseline variables

The following variables will be used to characterise the study population. The list includes variables that are measured post–randomisation and are therefore not, strictly speaking, baseline variables. We have chosen to include these variables in the list of baseline variables because they are unlikely to be affected by the intervention.

*Maternal Ethnicity:* Mandinka, Wollof, Fula, Jola, in The Gambia and Mossi, Gourounsi and Peulh in Burkina Faso.

*Maternal age:* median and interquartile range

*Apgar score (1–minute):* ≤3, 4–7, 8–10

*Birthweight (kg):* <1.5, 1.5–2.4, 2.5–3.9, 4.0+

*Sex of newborn:* male, female

*Mode of delivery:* vaginal, caesarean section (CS)

*Congenital malformation (visible):* yes, no

*Birth outcome:* live birth, fresh still birth, macerated still birth

### **Primary endpoint**

The primary endpoint is a composite endpoint of neonatal sepsis or death within 28 days of birth, excluding deaths (but not cases of sepsis) due to severe birth asphyxia, very low birth weight (VLBW) or a major congenital malformation.

We will use the following definitions of sepsis, severe birth asphyxia, very low birth weight (VLBW) and major congenital malformation:

#### *Neonatal Sepsis*

Cases of early- and late-onset sepsis will be identified using the clinical and laboratory criteria listed in Table 3. The list of criteria is the same as that used in Cutland et al. (2009), except that it does not include hypotension, because blood pressure is not routinely measured in babies in The Gambia and Burkina Faso. In addition, any hospitalised newborn who has a positive non-contaminated blood or CSF culture will be classified as a case. Note that the blood samples used to identify cases must have been collected during the same admission or at an OPD visit  $\leq 5$  days before the admission.

#### *Early-onset sepsis (days 0-3)*

At least one of the laboratory criteria in Table 3 and either: respiratory distress (one criterion required) or at least two clinical criteria recorded during an admission.

OR

A positive non-contaminated blood or CSF culture.

#### *Late-onset sepsis (days 4 - 28)*

At least one laboratory criterion and either: respiratory distress (two criteria required), OR one feature of respiratory distress and one other clinical criterion OR at least two other clinical criteria.

OR

A positive non-contaminated blood or CSF culture.

**Table 3** Criteria used in the definition of neonatal sepsis.

Clinical criteria	Definition
Respiratory distress	Respiratory rate >60 breaths/min or cyanosis or chest wall indrawing or grunting on expiration or respiratory distress noted in medical records
Pyrexia or hypothermia	Axillary temperature >38.0 °C, not attributable to external warming, or axillary temperature <36.0°C
Abdominal/feeding problems	Abdominal distension OR feeding intolerance (>20% residual over 24 hours), or poor feeding after feeding well, or 2 episodes of emesis
Bleeding diathesis	Defined as petechiae, echymosis, mucous membrane bleeding, pulmonary haemorrhage, or excessive oozing from venipuncture sites
Lethargy or irritability	Noted by medical staff in the absence of other central nervous system symptoms
Central nervous system	Seizures, or bulging fontanelle, or single witnessed episode of apnoea
Laboratory criteria	
White blood cell count (WCC)	WCC <5x10  /L OR >25x10  /L in the absence of receiving corticosteroids
Absolute neutrophil count (ANC)	ANC<1.75x10  /L or >15x10  /L
Platelet count	<150x10  /L
C-reactive protein	>10 mg/L (early-onset sepsis) >40 mg/L (late-onset sepsis)
Elevated CSF white blood cell (WBC) count	>30x10  /L WBC in the absence of significant red blood cells

*Severe birth asphyxia*

1-minute Apgar score ≤3.

*Very low birth weight*

Weight <1.5kg within 24 hours of birth.

*Congenital malformation*

Congenital malformations are identified by a study clinician and recorded either at delivery or discharge. Examples include: congenital heart defects, Down syndrome, craniofacial and musculoskeletal abnormalities such as encephalocele, cleft lip, cleft palate, talipes equinovarus. Only major congenital malformations (e.g. congenital heart defects, Down syndrome) will be excluded from the primary endpoint.

### **Secondary endpoints – neonate**

#### *Culture-confirmed sepsis*

A case of culture-confirmed neonatal sepsis will be recorded if a micro-organism that is not a common contaminant is isolated from either a blood or CSF sample. Culture-confirmed neonatal sepsis will be classified as either early-onset (0–3 days) or late-onset (4–28 days). The following bacteria will be considered contaminants: Coagulase-negative staphylococci, Micrococcus spp, Bacillus spp, Anthrobacter spp, Rhodococcus spp, Diphtheroids, Viridans streptococci.

#### *Malaria*

A child will be considered positive for malaria parasitaemia if he/she tests positive by microscopy or rapid diagnostic test during a hospital admission or OPD visit.

#### *Skin infection*

A skin infection will be recorded if either: i) a skin swab is taken during a hospital admission or OPD visit, or ii) any of the following diagnoses are recorded on a solicited AE (day 28), unsolicited AE, OPD visit, admission or discharge review form.

The Gambia:

“SKIN SEPSIS” or “SKIN INFECTION” or “PUSTULE(S)” or “IMPETIGO” or “FURUNCLE(S)” or “BOIL(S)” or “TREPONEMATOSIS” or “YAWS” or “CARBUNCLE(S)” or “ABSCESS(ES)” or “CELLULITIS” or “COLLECTION(S)” or “INFECTED ULCER(S)” or “WEN(S)” or “CANKER(S)” or “CYST(S)” or “ERYSIPELAS” or “NECROTISING INFECTIONS” or “CUTANEOUS ANTHRAX” or “CHANCRE”

Burkina Faso:

“FURONCLE” or “SEPTICEMIE CUTANEE” or “SEPSIS DE LA PEAU” or “POSTULE” or “IMPÉTIGO” or “TREPINOMATOSE” or “ESCARBOUCLE” or “INFECTION DE LA PEAU”

*Eye infection*

An eye infection will be recorded if either: i) an eye swab is done during a hospital admission or OPD visit, or ii) "PURULENT EYE DISCHARGE" (The Gambia) or "ÉCOULEMENT OCULAIRE PURULENTE" (Burkina Faso) is recorded on a solicited AE (day 28), unsolicited AE, OPD visit, admission or discharge review form.

*Umbilical infection*

An umbilical infection will be recorded if: i) an umbilical swab is done during a hospital admission or OPD visit or ii) "UMBILICAL CORD DISCHARGE" (The Gambia) or "OMPHALITIS" (The Gambia) or "ÉCOULEMENT AU NIVEAU DU CORDON OMBILICAL" (Burkina Faso) is recorded on a solicited AE (day 28), unsolicited AE, OPD visit or admission form.

*Ear infection*

An ear infection will be recorded if: i) an ear swab is done during a hospital admission or OPD visit or ii) "EAR DISCHARGE" or "OTITIS MEDIA" (The Gambia) or "OTITE" or "ÉCOULEMENT OREILLE" (Burkina Faso) is recorded on a solicited AE (day 28), unsolicited AE, OPD visit or admission form.

*Culture-confirmed non-invasive infections*

Skin, eye, umbilical and ear infections will be considered "bacterially-confirmed" if a swab is done during a hospital admission or OPD visit and a micro-organism that is not a common contaminant is isolated from the swab.

*Fever*

A case of fever will be recorded if an axillary temperature  $\geq 38.0$  °C, not attributable to external warming, is recorded in the neonate during an admission, OPD visit, or at the discharge review.

*Malnutrition*

Height, weight, MUAC and head circumference measurements at 6 and 12 months of age will be used to identify malnutrition in the anthropometrical cohort. WHO 2006 child-growth standards will be used to calculate Z-scores height-for-age (HAZ), weight-for-age (WAZ), weight-for-height (WHZ), head circumference-for-age, and

MUAC for age. Children with z-scores  $<-2SD$  and  $<-3SD$  will be classified as malnourished and severely malnourished, respectively.

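### Diagnosis terms for skin and umbilical infection differ by country, so unswabbed cases may be counted in The Gambia and missed in Burkina Faso

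*SAP*

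**What the plan says.** SAP section 4.4 (Secondary endpoints – neonate) gives each local infection two alternative routes to being a case.

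- **Swab route, the same in both countries.** For skin, it is enough that "a skin swab is taken during a hospital admission or OPD visit". Eye and umbilical infection have the parallel rule.
- **Text route, with separate lists by country.** For skin, a case is recorded if "any of the following diagnoses are recorded on a solicited AE (day 28), unsolicited AE, OPD visit, admission or discharge review form". The Gambian list ends with "WEN(S)” or “CANKER(S)” or “CYST(S)” or “ERYSIPELAS” or “NECROTISING INFECTIONS” or “CUTANEOUS ANTHRAX” or “CHANCRE". The Burkina Faso list has eight entries, among them "SEPTICEMIE CUTANEE" and then "POSTULE” or “IMPÉTIGO” or “TREPINOMATOSE” or “ESCARBOUCLE” or “INFECTION DE LA PEAU".

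For umbilical infection, the Gambian terms are cord discharge and omphalitis. Burkina Faso has a cord-discharge term only: "OMPHALITIS' (The Gambia) or 'ÉCOULEMENT AU NIVEAU DU CORDON OMBILICAL' (Burkina Faso". For eye infection each country has one term, and the two are translations of each other.

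Section 3.4 lists skin and umbilical cord infections as secondary neonatal endpoints, along with "Bacterial conjunctivitis". Section 6.3 plans exploratory analyses by country for every Primary-cohort outcome, and section 6.6 adds a Wald test of treatment by country.

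**The concern.** The text route is part of the case definition, so two lists of different breadth are two case definitions. A newborn with an abscess, cellulitis, erysipelas or an infected ulcer recorded on a form, and no swab, is a case in The Gambia. In Burkina Faso the same newborn is a case only if a broader listed term was also written. The same holds for omphalitis written as such.

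The spelling adds to this. POSTULE and TREPINOMATOSE look like misspellings of the French words for pustule and treponematosis, and no Burkina Faso term carries a plural. The antibiotic list in the same section does give variants (gentamicin and gentamycin), so the point was recognised elsewhere in the plan.

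At stake are the number of events and the precision for two secondary outcomes, and the meaning of any by-country table that shows their incidence. A gap between countries in such a table could reflect vocabulary as much as disease.

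**Working it through.** The SAP gives no figure on this point to reproduce. The check is a count of terms followed by an illustration of size.

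**1. Terms by country (SAP 4.4)**

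| Outcome | The Gambia | Burkina Faso |
|---|---|---|
| Skin | 20 (10 with a plural form) | 8 (none with a plural) |
| Umbilical | 2 | 1 |
| Eye | 1 | 1 |
| Ear | 2 | 2 |

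The country difference in length is confined to skin and umbilical infection.

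**2. Matching the skin terms**

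Eight Gambian terms have a French counterpart: skin sepsis, skin infection, pustule, impetigo, furuncle, boil, treponematosis and carbuncle. Here FURONCLE is taken to serve both furuncle and boil. The other 20 − 8 = 12 have none: yaws, abscess, cellulitis, collection, infected ulcer, wen, canker, cyst, erysipelas, necrotising infections, cutaneous anthrax and chancre. Of these, cyst, wen and collection are not infections as such.

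**3. Whom the difference can reach**

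The swab route needs an admission or OPD visit. A diagnosis made without a swab depends on the text list. That includes entries found only on the day-28 or unsolicited AE form or, for skin, the discharge review form. Section 4.1 says the day-28 interview was by telephone after 23 March 2020, so that contact could not itself yield a swab.

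**4. Size, as an illustration**

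Inputs:
- Burkina Faso share of women: 5,250/12,000 = 0.4375 (section 4.1).
- Capture *s* in Burkina Faso relative to The Gambia: 0.80 to 0.50. This is an assumption; the SAP gives no figure.
- Equal true incidence in the two countries: also an assumption.

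Results:
- Events lost overall = 0.4375 × (1 − *s*). This gives 0.4375 × 0.20 = 8.75% and 0.4375 × 0.50 = 21.9%.
- Width of the Burkina Faso interval. For a rare outcome the standard error of the log odds ratio scales as 1/√events, so the ratio is 1/√*s*: 1/√0.80 = 1.12 and 1/√0.50 = 1.41.
- Width of the pooled interval = 1/√(1 − loss): 1/√0.9125 = 1.05 and 1/√0.781 = 1.13.

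These apply *s* to all events. If 0.50–0.80 is instead the capture *c* of the text list alone, and a share *w* of Burkina Faso cases is swabbed, the loss is 0.4375 × (1 − *w*) × (1 − *c*). This is smaller for any *w* above zero. Hence upper bound, given equal incidence.

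**5. Effect on the treatment comparison**

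With equal capture by arm, the Burkina Faso risk ratio is (*s* × p₁)/(*s* × p₀) = p₁/p₀, which is unchanged. Taking control incidence 4%, RR 0.70 and *s* falling from 1.0 to 0.4, the pooled odds ratio moves from 0.691 to 0.694 and the Burkina Faso odds ratio from 0.691 to 0.697.

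Power with 6,000 per arm is Φ(|p₀ − p₁|/√[(p₀(1 − p₀) + p₁(1 − p₁))/6000] − 1.96). Here p₀ = p × (0.5625 + 0.4375*s*) and p₁ = RR × p₀. The values of p, RR and *s* are assumptions.

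| p, RR | *s* = 1.0 | 0.8 | 0.6 | 0.4 |
|---|---|---|---|---|
| 2%, 0.70 | 0.720 | 0.680 | 0.635 | 0.586 |
| 2%, 0.75 | 0.551 | 0.513 | 0.474 | 0.432 |
| 4%, 0.70 | 0.952 | 0.933 | 0.907 | 0.873 |
| 4%, 0.75 | 0.846 | 0.811 | 0.770 | 0.722 |

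Overcounting acts differently. If a fraction *f* of Gambian control-arm events are non-infections that treatment does not affect, the observed risk ratio there is RR × (1 − *f*) + *f*, which is closer to one. The SAP gives nothing from which to set *f*.

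**The case against.** The strongest reply has four parts.

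- **The text list is only one route.** Any swab at an admission or OPD visit makes a case in both countries, whatever was written. This stands. It limits the problem to unswabbed diagnoses and makes the loss figures upper bounds.
- **An undercount is not demonstrated.** The SAP does not say that matching is exact or that the fields are free text. The odd spellings may reproduce form options or database entries, and the general French term for skin infection may absorb some unlisted diagnoses. Part of any gap could be overcounting in The Gambia. This also stands, so the supportable word is *may*. It does not explain why abscess, cellulitis, erysipelas, infected ulcer and omphalitis are listed for one country only.
- **The treatment effect is safe.** The trial is double-blind, randomisation is stratified by facility (section 4.3), and the Primary-cohort models include country (sections 6.3 and 6.6). Lower capture should be equal by arm. This stands.
- **These are secondary outcomes, and the by-country analyses are exploratory.** True, and it sets the weight of the point. The primary endpoint is untouched.

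A reader might also infer that eye infections are undercounted in Burkina Faso. The document does not support that: "PURULENT EYE DISCHARGE' (The Gambia) or 'ÉCOULEMENT OCULAIRE PURULENTE' (Burkina Faso" are parallel single terms. The endpoint name in section 3.4 does differ from the eye-infection definition in 4.4, and conjunctivitis recorded without a swab or the discharge term is not counted. That applies equally in both countries.

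**Conclusion.** The point holds for skin and umbilical infection. The plan fixes case definitions that differ by country on the text route: 20 against 8 skin terms, and omphalitis for one country only. Nothing in the SAP explains the difference. Unswabbed diagnoses may therefore be counted in The Gambia and missed in Burkina Faso, and some Gambian terms may count non-infections.

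The cost is lost events, lost precision, and country-specific incidences of these two outcomes that are not comparable. If Burkina Faso captured 50–80% of events overall and true incidence were equal, 9–22% of all events would be lost and the Burkina Faso interval would be 12–41% wider. Both conditions are assumptions, and swab-detected cases would reduce the loss.

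Two stronger readings should be resisted. One is that the pooled treatment effect is materially biased: with capture equal by arm the risk ratio does not move and the odds ratio moves by about 0.003. The other is that the by-country analyses of all Primary-cohort outcomes are distorted: sepsis, mortality, malaria and antibiotic use have their own definitions, which do not use these lists.

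**What to change.** Before unblinding:

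1. Replace the two country lists for skin and umbilical infection with one list of concepts, each with matched English and French terms. Add French terms for abscess, cellulitis, erysipelas, infected ulcer and omphalitis, and give correct and variant spellings and plurals.
2. Drop cyst, wen and collection, or justify keeping them, with the same decision for both countries.
3. Extract all distinct recorded diagnosis strings from the named forms, map them to the concepts blind to arm, and state the matching rule in the SAP.
4. Separately, and not as a country difference, reconcile the endpoint name in section 3.4 (bacterial conjunctivitis) with the eye-infection definition in section 4.4.

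The cost is an edit to the SAP and a short blinded review of text strings. No new data are needed.

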### **Secondary outcomes**

The secondary outcomes are all binary and will therefore be analysed using logistic regression as described for the primary outcome (except the specific aetiologies of sepsis which will be analysed using Fisher's exact test because these are rare outcomes).

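### The Gambian skin-infection list counts a bare record of a cyst or wen as an infection, although it requires ulcers to be infected

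*SAP*

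**What the plan says.** SAP section 3.4 lists the endpoint among ten neonatal secondary endpoints: "6. Skin infections".

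Section 4.4 (Skin infection) gives two routes to becoming a case. One is that a skin swab was taken. The other is that "any of the following diagnoses are recorded on a solicited AE (day 28), unsolicited AE, OPD visit, admission or discharge review form". One listed term on one form is enough.

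The terms come as separate lists by country:

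- **The Gambia, 20 terms.** One stretch reads "INFECTED ULCER(S)” or “WEN(S)” or “CANKER(S)” or “CYST(S". A little before it stands "CELLULITIS” or “COLLECTION(S".
- **Burkina Faso, 8 terms,** ending "IMPÉTIGO” or “TREPINOMATOSE” or “ESCARBOUCLE” or “INFECTION DE LA PEAU". It has no counterpart to cyst, wen, canker or collection.

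The same section defines a separate, bacterially confirmed category of skin, eye, umbilical and ear infections, which needs a non-contaminant isolate from a swab. Section 8.1 (Secondary outcomes) sets the analysis: "The secondary outcomes are all binary and will therefore be analysed using logistic regression as described for the primary outcome".

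**The concern.** An endpoint named skin infection should count infections. *Cyst* and *wen* name lesions that may or may not be infected, and the rule asks for no further sign. The authors evidently saw this difficulty for ulcers, because they required the word *infected* there. The eye rule in the same section similarly asks for a purulent discharge. The qualifier was left off cyst and wen.

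A single oral dose of azithromycin has no evident way to prevent a non-infectious lesion. Under randomisation such lesions should be equally frequent in both arms. They then add the same amount to the numerator of each arm's risk, so any real effect on infection looks smaller and is harder to detect. What is at stake is the accuracy of one secondary estimate, not the trial's main conclusion.

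**Working it through.** **1. Text check.** Four questions settle whether the rule does what is claimed.

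- *Does a bare cyst or wen record make a case?* Yes. The second route needs one listed diagnosis, and both words are listed without a qualifier.
- *Is infection required elsewhere in the list?* Yes, for ulcers.
- *Does the bacterially confirmed category remove these records?* No. It is an additional label. An unswabbed cyst stays in the skin-infection endpoint.
- *Does the SAP provide for adjudication of matched records?* It describes none.

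**2. Is there a figure to reproduce?** No. The SAP gives no rate, effect size or power for skin infections, and no count for any listed diagnosis. Everything below is illustration on assumed values.

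**3. Dilution in The Gambia.** Let *p* be the true infection risk on placebo, *f* the risk of becoming a case only through a non-infectious cyst or wen record (the same in both arms), and *R* the true risk ratio. Then

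observed RR = (R·p + f)/(p + f) = (1 − q)·R + q, where q = f/(p + f) is the share of placebo-arm cases that are false.

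With R = 0.60 (assumed):

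| q (assumed) | calculation | observed RR |
|---|---|---|
| 1% | 0.99 × 0.60 + 0.01 | 0.604 |
| 5% | 0.95 × 0.60 + 0.05 | 0.62 |
| 10% | 0.90 × 0.60 + 0.10 | 0.64 |

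The SAP reports odds ratios. At risks of a few per cent these lie close to risk ratios and move the same way.

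**4. Both countries pooled.** Section 4.1 gives 6750 of 12,000 women in The Gambia, a share of 0.5625. If the true risk is the same in both countries (assumed) and false cases arise only in The Gambia, put r = 0.5625 × q/(1 − q). Then pooled RR = (0.60 + r)/(1 + r).

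- q = 1%: r = 0.0057, RR = 0.602
- q = 5%: r = 0.0296, RR = 0.611
- q = 10%: r = 0.0625, RR = 0.624

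**5. Power.** Two-sided 5% test, power = Φ(|p₁ − p₂|/SE − 1.96), SE = √{[p₁(1 − p₁) + p₂(1 − p₂)]/n}. Here R = 0.70 is assumed, and n = 6750/2 = 3375 per arm in The Gambia or 6000 per arm overall.

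- The Gambia, p = 3%, f = 0.25% (q = 0.25/3.25 = 7.7%): 3.25% against 2.35%, observed RR 0.72; power falls from 0.65 to 0.61.
- The Gambia, p = 5%, f = 0.5% (q = 0.5/5.5 = 9.1%): 5.5% against 4.0%, observed RR 0.73; power falls from 0.86 to 0.83.
- Pooled, p = 3%, f = 0.25% in The Gambia only: power falls from 0.88 to 0.86.

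**6. Type I error.** If R = 1, the observed RR is (p + f)/(p + f) = 1. Balanced false cases do not create a spurious effect.

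**The case against.** The best case for leaving the list alone has four parts.

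*The terms sit under the heading Skin infection and are called diagnoses.* A clinician completing a newborn's form may write *cyst* for an infected swelling, and the SAP does not show local recording practice. This is fair, and it is why the size cannot be known. It does not change the stated rule, which also counts the uninfected lesion.

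*The definition looks deliberately broad.* A swab merely being taken is enough, and a stricter bacterially confirmed category stands beside it. A sensitive definition paired with a specific one is a legitimate design. But it does not explain why ulcers carry a qualifier and cysts do not.

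*Few newborns would be cases only through these words.* Anyone who also had a swab or another listed diagnosis is a case regardless and adds nothing to q. This stands, and the true share may be near the bottom of the range shown.

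*The consequence is limited.* This is one of ten neonatal secondary endpoints and no decision rule in the SAP depends on it. This stands too.

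Stronger readings are tempting but not supported:

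- A reader might treat *collection* and *canker* as equally non-infectious. *Collection* follows abscess and cellulitis in the list and plausibly means pus; *canker* is ambiguous.
- A reader might suppose that a cyst at any body site would be swept in. The SAP does not describe this endpoint as a literal text search.
- A reader might infer that the terms distort the comparison between countries. They are indeed Gambia-only, but so are abscess, cellulitis and erysipelas. The lists would remain non-parallel without cyst and wen, and section 6.3 already calls the country analyses exploratory.

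**Conclusion.** The point holds as a small defect of definition. As written, a Gambian newborn with a bare cyst or wen record is a skin-infection case, contrary to the list's own treatment of ulcers. The resulting bias runs towards no effect, provided such lesions are balanced by arm.

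Its size cannot be derived from the SAP. With an assumed 1% to 10% of Gambian placebo-arm cases arising only from these terms, a true RR of 0.60 would be seen as about 0.60 to 0.64 in The Gambia and about 0.60 to 0.62 pooled. In the power examples, which assume a true RR of 0.70, the loss is two to four percentage points. A larger share of false cases, and so a larger bias, could be imagined, but nothing in the SAP supports one. The primary endpoint and type I error are untouched. This is worth correcting because it is cheap, not because it threatens the trial.

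**What to change.** In the Gambian list in section 4.4, count *cyst* and *wen* only when the record also states infection or pus, in line with the ulcer term. Before the code is broken, re-read blinded all records matched only by these two terms. In the same pass, check records matched only by *collection* or *canker*, and keep those that denote pus or skin infection. Pre-specify a sensitivity analysis using the list as it is now written.

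The cost is a line or two of SAP wording, a blinded re-read of what are probably few records, and one extra model. The downside is that a few true infections recorded loosely may be lost; the sensitivity analysis would show whether that matters. The change does not make the two country lists equivalent and should not be presented as doing so.
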